4. Research Design and Methods

Methods

Patients presenting to the Emergency Department with pain will be screened for inclusion into one of four groups:

1. Headache: Non-traumatic headache of less than four days duration.
2. Trauma: Patients with acute mild to moderate musculo-skeletal injury (no trauma activation) or pain of less than four days duration.
3. Colic/Abdominal pain: Patients with mild to moderate abdominal or flank pain of less than four days duration.
4. Viral syndrome: Patients with less than four days of generalized systemic complaints suggestive of an acute viral syndrome.

A pregnancy test will be administered to females of childbearing potential before administration of the study drug. Patients will be randomized to receive either 30mg of ketorolac, 10mg of ketorolac, or saline as a slow intravenous infusion over 10 minutes via a pump. Thirty minutes or later their pain score will be re-evaluated, they will be assessed for any negative effects of the treatment, additional pain medications will be offered if indicated, and the patient's involvement in the study will be concluded.

Data collected:

1. Patient demographics
 - a. Age
 - b. Sex
 - c. Complaint
2. Pain scores
3. Side effects noted by patient or staff

5. Subjects

Subjects will be eligible for recruitment when they present to the Emergency Department with a chief complaint consistent with the four study groups. Inclusion criteria will be:

1. Age \geq 18y/o
2. Not pregnant or lactating (negative urinary pregnancy test)
3. No contraindication to ketorolac

Exclusion criteria

1. Age $<$ 18y/o
2. Pregnancy or lactation
3. Contraindication to ketorolac

If the subjects are eligible for inclusion they will be offered inclusion in the study by one of the Emergency Department faculty. If they refuse participation they will be treated in a standard fashion.

6. Treatment of subjects

There will be no long term follow up of patients for data. Subjects who have incomplete data will have their data discarded and removed from enrollment.

7. Statistics

End point: the primary hypothesis is that ketorolac has different effects depending on the dose and the condition. We will compare pain scores at 30 minutes or after for each of the doses and the groups.

Sample size: We plan to enroll 170 patients in each group. This is based on a change in pain scale of 2.5 with a standard deviation of 2.5, and α of 0.05 and power of 0.80[5].

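### Section 7 ties one primary hypothesis to three arms in four conditions with 0.05 as the only alpha and no testing rule; reading all 12 pairwise comparisons at 0.05 would give about a 40% chance of a false dose difference if ketorolac equals saline throughout

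*Combined protocol and SAP*

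**What the plan says.** Section 4 (Research Design and Methods) says that patients "will be screened for inclusion into one of four groups": headache, trauma, colic or abdominal pain, and viral syndrome. It then says "Patients will be randomized to receive either 30mg of ketorolac, 10mg of ketorolac, or saline". Section 3 (Objectives and Purpose) gives the aim as finding the best dose in each of those four groups, which are expected to respond through different mechanisms.

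Section 7 (Statistics) sets a single hypothesis: "the primary hypothesis is that ketorolac has different effects depending on the dose and the condition". The analysis is one sentence: "We will compare pain scores at 30 minutes or after for each of the doses and the groups". The sample size follows: "We plan to enroll 170 patients in each group", based on "a change in pain scale of 2.5 with a standard deviation of 2.5" "and α of 0.05 and power of 0.80". That 0.05 is the only significance level in the document.

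Section 7 names no test or model and no primary contrast. It gives no order of testing, no overall test that must pass first, and no adjustment for several comparisons. It does not say whether tests are one-sided or two-sided.

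**The concern.** The trial sets out to make dose statements condition by condition, under one primary hypothesis. That hypothesis can be supported by a dose difference in any of the four conditions and between any two of the three treatments. With no rule fixed in advance, the choice of which comparisons count, and at what level, stays open until the data are seen.

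The chance pattern also resembles the hypothesis. Of simulated trials with no effect anywhere that still gave at least one significant pairwise result, 81% gave it in exactly one condition. A difference in one condition and none in the others is what effects that vary by dose and condition would look like, so a chance finding would be read as confirmation. Dosing advice for a heavily used drug could then rest on it.

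**Working it through.** **Inputs.** Four conditions and three arms (Section 4). Alpha 0.05, power 0.80, difference 2.5, SD 2.5, and 170 per group (Section 7). Assumed because not stated: two-sided tests, 1:1:1 allocation, and group meaning condition as in Section 4. That gives 170/3 = 56.7 per arm, or 57/57/56.

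**The plan's own figure.** Per arm, n = 2 × (1.960 + 0.842)² × (2.5/2.5)² = 15.7, so 16 (17 by t-test). That is 3 × 16 = 48 per condition (51 by t-test) and 12 × 16 = 192 over all 12 cells (204 by t-test). The stated 170 is not reproduced. That is a separate matter, because the error rates below barely depend on sample size: pairwise t-test simulations at 14 to 170 per arm all give 40.4% to 40.6%.

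**Number of comparisons.** Three arms give 3 pairs, and 3 × 4 conditions = 12.

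**One condition, no true difference.** At least one of three pairwise tests is significant when the range of three independent standard normal means exceeds 1.960 × √2 = 2.772. From the studentized range distribution (three means, infinite degrees of freedom) this probability is 0.1223. It allows for the correlation among contrasts that share an arm.

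**Four conditions.** These are separate patients, so 1 − (1 − 0.1223)⁴ = 0.406. Simulating null trials with t-tests at 57/57/56 gives 40.5%. Treating all 12 tests as independent would give 1 − 0.95¹² = 0.460, which is too high.

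**Other readings of the same sentence, each test at 0.05:**

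| Reading | Chance of at least one false positive |
|---|---|
| All 12 pairwise tests | 40.6% |
| Each dose versus saline only (9.05% per condition) | 1 − (1 − 0.0905)⁴ = 31.6% |
| One overall test per condition | 1 − 0.95⁴ = 18.5% (simulated 18.2%) |
| Only 10 mg versus 30 mg, one test per condition | 1 − 0.95⁴ = 18.5% (simulated 18.3%) |
| All three pairs, one condition alone | 12.2% |
| One global or interaction test | 5% |

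The 10 mg versus 30 mg row also applies to all 12 tests if both doses work equally, because the contrasts with saline are then true differences.

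**Gated rule at a flat 0.0125.** If all three arms are equal in a condition, the overall test limits the error to 0.0125. If exactly one arm differs, one true null pair remains and is tested at 0.0125. If all three differ, there is nothing to reject falsely. Each condition therefore contributes at most 0.0125, and 1 − (1 − 0.0125)⁴ = 4.9%. Simulation gives 4.6% to 4.8%.

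**Gated rule with Holm-graded levels.** Here the pairwise tests inherit 0.0125, 0.0167, 0.025 and 0.05 as successive overall tests pass. With both doses better than saline by 2.5 points and equal to each other in every condition, simulation gives 8.6%. Holm moves alpha on once an overall test rejects, but the pairwise tests in that condition then spend it again.

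**Cost in power.** For 2.5 points with SD 2.5 and 57 versus 56 patients, noncentral-t power of a pairwise test is 99.95% at 0.05 and 99.7% at 0.0125. The difference detectable with 80% power is 2.5 × (1.960 + 0.842) × √(2/56.7) = 1.32 at 0.05 and 2.5 × (2.498 + 0.842) × √(2/56.7) = 1.57 at 0.0125 (1.33 and 1.59 by t-test). If 170 instead meant patients per dose arm, there would be 42.5 per cell, and the same formula gives 1.52 and 2.5 × 3.340 × √(2/42.5) = 1.81.

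**The case against.** The strongest reply is that Section 7 never says it will run 12 unadjusted t-tests or claim success on any one of them. It says only that scores will be compared. A single global or interaction test would fit the stated hypothesis and hold 5%. A reader might infer from the 12-test arithmetic that this trial has a 40% false-positive rate. The documents do not support that. The figure needs unadjusted two-sided pairwise tests, a claim on any one result, and ketorolac no better than saline in all four conditions. If ketorolac works equally at both doses, the figure is about 18%. The Background section itself cites a study reporting equal efficacy across three intravenous doses, so that case is realistic. This part of the objection stands and limits what can be said.

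A second reply is that the four conditions are four parallel questions, each with its own enrolment, so no adjustment across them is needed. Section 3 gives this some support. It is weakened by Section 7, which places everything under one primary hypothesis, and it does not rescue the plan: three pairwise tests in a single condition already carry 12.2%.

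A third reply is that the missing primary test is the root defect and multiplicity only follows from it. That is fair, and it is why the fix names the test as well as the level.

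**Conclusion.** The concern holds in conditional form. One primary hypothesis is tied to comparisons of three arms in four conditions with "α of 0.05 and power of 0.80" and nothing that fixes which comparisons count. The chance of a false dose difference at the final analysis is about 40% if all 12 pairwise comparisons are read at two-sided 0.05, any one supports a claim and ketorolac equals saline everywhere. It is about 18% with one overall test per condition, or with two equally effective doses, and 12% within one condition under the pairwise reading. Among the readings examined, only a single global or interaction test holds 5%, and the plan does not specify one.

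These figures assume 1:1:1 allocation and do not depend materially on what 170 per group means. They exclude the interim look at half enrolment. If that look also used an unadjusted 0.05, the 12-comparison figure would rise to about 58%; that is a separate point. This should be corrected before analysis, because the choice of test otherwise remains open when the data are seen.

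**What to change.** State the following in Section 7.

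1. In each condition, compare the three arms with one overall test at 0.0125 (0.05/4).
2. Only if that test passes, run the three pairwise tests in that condition, each also at 0.0125. Do not pass Holm-graded levels down to the pairwise tests: the calculation above shows that this does not hold 5%.
3. Base any statement that the effect depends on condition on one dose-by-condition interaction test, not on significance in one condition and its absence in another. State its level. The 5% in steps 1 and 2 covers the 12 dose comparisons and not this further claim, so Section 7 should also say which is primary, or share the 0.05 between them.
4. Report all other contrasts as estimates with 95% intervals, without a significance claim.
5. State that tests are two-sided and give the allocation ratio.

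The cost is a few sentences and no extra patients. At about 57 per arm, power for 2.5 points falls from 99.95% to 99.7%, and the difference detectable with 80% power rises from about 1.3 to 1.6 points, still below the planned 2.5. These power figures are for the pairwise test alone; requiring the overall test to pass first can only lower power for smaller differences. The rule covers the final analysis only, so the interim look needs its own stopping boundary.

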An interim analysis will be performed when half of the patients are enrolled in each group. The study will be terminated if there is significant difference in the groups at this point. [name] is providing statistical support for the project.

8. Direct access to source data/documents

Access to source data and documents will be provided by the investigators for any auditing or monitoring or reviews by the IRB/IEC, or regulatory inspections.

9. Ethics

This trial proposes to study the proper dosing of ketorolac in several different conditions and attempts to clarify the placebo effect in this setting. Standard care will not be withheld at any time during this protocol. The intervention may offer significant benefit for the patients being studied. An interim analysis is planned with termination of the study if this is the case.

10. Data handling and recordkeeping

Initial data collection will include identification of the patient by name and medical recorded number. This data will be kept in a locked cabinet in the Emergency Medicine Department. Data will be extracted from these records and recorded in a computer data base and identified only by subject number. No patient identifiers will be entered in to the computer database.

11. Investigators

[name]: [name] is Pharm.D. with extensive training in the clinical use of the medications involved in this study and a [history of working in the emergency department](#).

[name]: [name] is Pharm.D. with extensive training in the clinical use of the medications involved in this study whose clinical duties are in the Emergency Department.

[name]: [name] is an Associate Professor of Emergency Medicine. He is attending physician in the Emergency Department and routinely manages patients with headache.

[name]: [name] is Research Assistant Professor in the Department of Emergency medicine and has extensive training in research.

12. Financing and insurance

Patients will have regular charges for Emergency Department visit but will not be charged for ketorolac/placebo or its administration. Charges for any treatment will be per usual. There will be no payments to the subjects.

13. References

1. Patrick, P.A., et al., *Timely pain management in the emergency department*. Journal of Emergency Medicine, 2015. **48**(3): p. 267-73.
2. Catapano, M.S., *The analgesic efficacy of ketorolac for acute pain*. Journal of Emergency Medicine, 1996. **14**(1): p. 67-75.

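### The half-enrolment look can end the study on a significant difference, but Section 7 sets no interim level, no adjusted final level and no trigger contrast; with 0.05 at both looks, one comparison carries a type I error of 6.7% to 8.3%

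*Combined protocol and SAP*

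**What the plan says.** Section 7 (Statistics) sets the timing, "An interim analysis will be performed when half of the patients are enrolled in each group", and the consequence, "The study will be terminated if there is significant difference in the groups at this point". Section 9 (Ethics) returns to the rule in different terms: "The intervention may offer significant benefit for the patients being studied", and then "An interim analysis is planned with termination of the study if this is the case".

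On the analysis itself, Section 7 states that "the primary hypothesis is that ketorolac has different effects depending on the dose and the condition" and that "We will compare pain scores at 30 minutes or after for each of the doses and the groups". On size it says "We plan to enroll 170 patients in each group" and "This is based on a change in pain scale of 2.5 with a standard deviation of 2.5", with alpha 0.05 and power 0.80. That is the only alpha in the documents. It belongs to the sample-size statement, and its sidedness is not given.

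Neither section names a boundary, an alpha-spending rule, an adjusted final level, a test or a contrast for the interim decision.

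**The concern.** Two things are missing from a rule that decides whether the trial continues.

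**The level.** A look that can stop the trial on significance is a second chance to reject. Unless the two looks share the alpha, the overall error exceeds the stated 0.05, even for one comparison.

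**The trigger.** Sections 3 and 4 use *groups* for the four pain conditions, and the end-point sentence in Section 7 sets the doses beside the groups. Taken literally, the stopping sentence could be met by headache and trauma patients having different pain scores, which is not a randomised comparison. Section 9 points instead to ketorolac against saline. The objective in Section 3 is the optimal dose, which points to 10 mg against 30 mg. These readings give different stopping decisions. The plan also does not say whether a result in one condition ends the whole study.

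At stake are the stated error rate and the dose question. A stop caused by a saline difference would close the 10 mg versus 30 mg comparison at half its planned size. Section 2 cites a study finding 10, 15 and 30 mg equally effective, so a small dose difference is plausible on the plan's own background.

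**Working it through.** **Inputs from the documents.** Alpha 0.05, power 0.80, difference 2.5, SD 2.5 and 170 per group (Section 7); one look at half enrolment (Section 7); three arms and four conditions (Section 4). **Assumed:** two-sided testing unless stated, equal allocation, information fraction 0.5.

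**1. The plan's own figure.** For two arms, n = 2 × (1.96 + 0.84)² × (2.5/2.5)² = 15.7, so 16 per arm. That is 48 for three arms and 192 for all twelve arm-by-condition cells. The 170 is not reproduced. This is a separate matter: steps 2 and 3 do not use the sample size.

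**2. One comparison at 0.05 at both looks.** Under no effect, the interim and final statistics Z1 and Z2 are bivariate normal with correlation √0.5 = 0.707.

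- Two-sided, stop in either direction: 1 − P(|Z1| < 1.96 and |Z2| < 1.96) = 0.0831. Each look rejects with probability 0.05, so both reject with probability 0.05 + 0.05 − 0.0831 = 0.0169.
- Interim stop for benefit only, two-sided final test: by symmetry half of that overlap applies, so 0.025 + 0.05 − 0.0169/2 = 0.0666, or 6.7%.
- One-sided 0.05 at both looks: 1 − P(Z1 < 1.645 and Z2 < 1.645) = 0.0801.
- If the look falls at 40% or 60% of the information, the two-sided figure is 8.6% or 8.0%.

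Several unadjusted comparisons raise the error further, but most of that is present without the look: for all twelve within-condition dose pairs, simulation gives at least one false positive in 41% of trials at the final analysis alone and 58% with the look.

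**3. A boundary that holds 0.05.** O'Brien-Fleming critical values at half and full information are z = 2.797 and 1.977, that is p<0.0052 and p<0.048. The same bivariate calculation gives 0.0500 overall.

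**4. What a half-size stop leaves for 10 mg versus 30 mg.** Half-width = t × 2.5 × √(2/n), where t is the 97.5% point on 2n − 2 degrees of freedom. With 170 per condition split three ways, n is about 57 per arm at the end and 28 at the look:

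- n = 28: 2.005 × 2.5 × √(2/28) = 1.34 points
- n = 57: 1.981 × 2.5 × √(2/57) = 0.93 points

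Power at the look from a t test at 0.05, by layout:

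| Layout | Per arm at look | Half-width | Power, 1.0 point |
|---|---|---|---|
| 170 per condition, one condition | 28 | 1.34 | 0.31 |
| 170 per arm | 85 | 0.76 | 0.74 |
| 170 per condition, four conditions pooled | 112 | 0.66 | 0.85 |

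The 1.0-point difference is an assumption for illustration. At the full 57 per arm its power is 0.56. For the 2.5-point difference in Section 7, power at 28 per arm is 96%.

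**The case against.** The best reply has four parts.

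*The investigators may intend a stricter interim level.* They may, and the error figures are therefore conditional on using 0.05 at both looks. But no other level is stated, so the written plan offers nothing else to apply. A reader might infer that the level was left open in order to be chosen after seeing the data. The documents do not say when the choice would be made, so that inference is unsupported.

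*Section 9 describes a stop for benefit, so counting stops in both directions overstates the error.* This stands. On that reading the figure is 6.7%, which is still above 5%.

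*Multiplicity over doses and conditions exists anyway.* This also stands. A reader might take 58% as the damage done by the interim look. The plan names no such set of tests, and 41% would arise with no look at all.

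*The trial is large for its design effect, so an early stop does little harm.* This is right for a 2.5-point difference. The loss of precision matters for smaller dose differences within a condition, and it shrinks if 170 is per arm or the conditions are pooled. It would be too strong to say that an early stop ruins the dose comparison.

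**Conclusion.** The point holds in this form. The interim look is binding and has no level, no matching final level and no identified contrast. Applying the only stated alpha at both looks gives 8.3% for one two-sided comparison, 8.0% one-sided, or 6.7% with a benefit-only stop and a two-sided final test. These figures assume a look at half the information and do not depend on what 170 per group means.

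The documents do not establish that the trial will run at 8.3%, because they do not say that 0.05 applies at the interim. What they establish is that control at 0.05 is not secured and that the event that stops the study cannot be identified.

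The effect on the dose comparison is secondary and depends on layout: 1.34 instead of 0.93 points per condition under 170 per condition and equal allocation, and less under the other layouts. The point should be settled before the interim analysis because the rule decides whether the trial continues.

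**What to change.** By protocol amendment, before interim data are opened:

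1. In the stopping sentence of Section 7, replace *groups* with *dose arms*. Name the one randomised dose-arm test that is the interim trigger, and state whether it acts on a single condition or on the whole study.
2. Give that test an O'Brien-Fleming boundary: p<0.0052 at half enrolment and p<0.048 at the end, 0.05 overall (two-sided).
3. Reconcile the Section 7 trigger with the benefit statement in Section 9 and with the optimal-dose objective. State what becomes of 10 mg versus 30 mg if the trigger is a saline difference.

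If the look has already taken place, which the documents do not say, report that it was unadjusted and state the resulting type I error for the test and direction actually used.

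**Cost.** No extra patients. With 57 per arm (normal approximation), the boundary moves power from 57.0% to 56.6% for an assumed 1.0-point difference and from 89.3% to 89.1% for 1.5 points. Splitting alpha over the four conditions would cost more, but that is the price of multiplicity at the final analysis and a separate decision.

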Study Title: Dosing of ketorolac

NCT: NCT03464461

Date: 5/12/2021

Dosing of ketorolac

[name] Pharm.D., [name] PhD., [name] MD

05/12/2021 v6

1. Objective and Specific Aims

The non-steroidal anti-inflammatory drugs (NSAID's) are very commonly used to treat pain in Emergency Departments. In January of 2018 more than 1100 doses of the injectable NSAID ketorolac were given in the University of Missouri Emergency Department. The correct dosing of ketorolac is unclear.

Our study is designed to clarify the optimal dose of ketorolac.

2. Background and Significance

Background

Optimal pain management in the Emergency Department remains problematic[1]. NSAID are a particularly useful class of drugs in Emergency Departments because of their effectiveness and safety[2]. The parenteral form of ketorolac has become particularly popular for treatment of acute pain in Emergency Departments, demonstrated by the total of more than 1100 doses given in the University of Missouri Emergency Department in January of 2018 (internal audit).

Recently the optimal dosing of ketorolac has been questioned[3]. This study showed equal efficacy among three doses of intravenous ketorolac: the standard 30mg dose, 15mg, and 10mg. These investigators recommended a change in practice to adopt the 10mg dose as standard.

Significance

The correct dosing of analgesics and ketorolac is actually a complicated and poorly understood issue. Ketorolac, as with other NSAID's, has multiple properties that may influence its analgesic properties; it has anti-inflammatory properties similar to other NSAID, is an analgesic, and is an inhibitor of prostaglandin synthesis[2]. Also it has significant placebo effect in some circumstances. In a study of acute headaches in an Emergency Department three intramuscular injections were compared: meperidine 50mg with 25mg promethazine, ketorolac 60mg, and saline[4]. The three treatments were found to be effective and equivalent. The authors conclude that the placebo effect was so profound that analgesic effects could not be evaluated. There is also evidence that ketorolac and other NSAID's have different efficacy as a function of

the type of pain[2]; that is, that pain which is inflammation mediated may be more very responsive.

3. Objectives and Purpose

This study is designed to determine the optimal dose of ketorolac in four groups of patients that would be expected to have different mechanisms of response to NSAID's.

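### The interim rule names no contrast or scope, so a ketorolac-versus-saline result can end the 10 mg versus 30 mg comparison in all four conditions

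*Combined protocol and SAP*

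**What the plan says.** Section 3 gives the purpose: "This study is designed to determine the optimal dose of ketorolac in four groups of patients". Section 4 sets three arms: "Patients will be randomized to receive either 30mg of ketorolac, 10mg of ketorolac, or saline". The allocation ratio is not given. In Section 7, "the primary hypothesis is that ketorolac has different effects depending on the dose and the condition", and the size is "We plan to enroll 170 patients in each group".

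The interim rule is also in Section 7. On timing: "An interim analysis will be performed when half of the patients are enrolled in each group". On action: "The study will be terminated if there is significant difference in the groups at this point". Section 9 returns to it. After the statement "The intervention may offer significant benefit for the patients being studied", it adds: "An interim analysis is planned with termination of the study if this is the case".

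Neither section gives a test, a significance level, a contrast or a condition for the decision. Neither provides for one arm or one condition to stop while the rest continue.

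**The concern.** The rule acts on the whole study, while the objective is a dose choice within each of four conditions. In a trial with a saline arm, Section 9 is most naturally met when ketorolac beats saline. That result does not distinguish 10 mg from 30 mg, and a result in one condition does not settle the others. Yet following the rule could halt all of them.

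This is separate from the question of interim alpha. A properly adjusted boundary would make a stop rarer, but it would still let a contrast unrelated to dose end the dose comparison. At stake is the precision of the 10 mg versus 30 mg estimate in every condition.

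**Working it through.** **Inputs.** From Section 7: 170 per group, difference 2.5, SD 2.5, alpha 0.05, power 0.80, one look at half enrolment. From Section 4: three arms, four conditions. Assumed because the plan is silent: 170 is per condition, allocation is 1:1:1, tests are two-sided t tests, scores are normal, nothing is lost, and the two doses have equal effect.

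**The plan's own figure.** For two means, n per arm = 2 × (1.960 + 0.842)² × (2.5/2.5)² = 15.7, so 16 (17 with the t distribution). Three arms need 48 to 51 per condition. The stated 170 is not reproduced. That is a separate matter and nothing below depends on why 170 was chosen.

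**Numbers at each stage.** 170/3 ≈ 57 per arm per condition at the end, and about 28 at the look.

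**Chance that a saline contrast is significant at the look.** With 28 per arm, the standard error of a difference is 2.5 × √(2/28) = 0.668. A single dose-saline test has power 95.7% for a true difference of 2.5 and 45.1% for 1.25. There are two such tests per condition sharing one saline arm, so the chance that at least one is significant was simulated:

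| True difference from saline | Level | One condition | Any of four |
|---|---|---|---|
| 2.5 | 0.05 | 99% | about 100% |
| 1.25 | 0.05 | 61–62% | 98% |
| 1.0 | 0.05 | about 45% | about 92% |
| 2.5 | 0.0054 | 91% | about 100% |
| 1.25 | 0.0054 | 27% | 70% |

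The last column assumes the same effect in every condition and that any one significant test stops the study. For example, 1 − (1 − 0.62)⁴ = 0.98. If only one condition has the effect, the one-condition column is a floor for the chance of a stop under that reading.

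**Chance that the dose contrast is significant.** With equal doses, 10 mg versus 30 mg is significant at 0.05 in about 5% of trials per condition. Under these assumptions, then, a stop would come mostly from saline.

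**What a stop costs the dose comparison, per condition.** The 95% half-width is t × 2.5 × √(2/n).

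- At the look: 2.005 × 0.668 = 1.34.
- At full size: 1.981 × 2.5 × √(2/57) = 1.981 × 0.468 = 0.93.
- Power for a 1.25-point dose difference: 45% at the look, 75% at full size.
- Power for a 2.5-point dose difference: 96% at the look, above 99% at full size.

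**If 170 means per arm.** The look then has 85 per arm. One dose-saline test is significant with probability about 100% for 2.5, 90% for 1.25 and 74% for 1.0. The dose half-width is 1.96 × 2.5 × √(2/85) = 0.75 instead of 0.53. The loss is smaller in points, but the rule is at least as easily triggered.

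**The case against.** A reader might infer that the trial is bound to stop by showing again that ketorolac beats saline, with the dose question unanswered. The documents do not support that, for four reasons.

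- **The rule is vague.** The plan uses the word groups mainly for the four conditions, including in the sentence just before the rule. A stop on either dose beating saline in any one condition is one reading, not the text. This stands as a limit on the claim, but it does not rescue the rule. A stop on a difference between conditions would be just as unrelated to dose, and Section 9 supports the benefit reading.
- **Benefit is not assured.** Section 9 says only that it may occur, and Section 2 cites a headache study in which ketorolac and saline were equivalent. Section 9 also lists clarifying the placebo effect as an aim, so a saline result has value of its own. All of this stands. The any-of-four figures also assume a uniform effect, while the primary hypothesis expects effects to differ by condition.
- **Half size is not uninformative.** Power for a dose difference equal to the planning value is still 96%, above the 80% target. If the look waits until every condition is half enrolled, each has about half its data. This stands. The loss concerns smaller dose differences, for which the plan sets no target.
- **Dropping the saline arm by condition is a real design change.** It affects randomisation and drug supply. This stands, so it is offered below only as an option.

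**Conclusion.** The concern holds in this form: the interim rule is undefined in contrast and scope, and as written it allows a result unrelated to dose to end the dose comparison in all four conditions. That works against the stated objective and is more than a missing detail.

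How likely such a stop is depends on the true saline difference and on how the rule is read. It is near certain at the planning value of 2.5. In a single condition it falls to about 45% at 1.0, and to 27% at 1.25 with a strict interim level. The cost is an interval about 1.4 times as wide (1.34/0.93) and a drop of 30 percentage points in power for a 1.25-point dose difference. Differences of that smaller kind matter here because Section 2 cites a study reporting equal efficacy of 10, 15 and 30 mg.

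These figures rest on 170 per condition, equal allocation, SD 2.5, equal doses and two-sided tests. The gap in the rule does not depend on them. Because large dose differences would still be detected and a stop is not certain, this should be fixed but is not disqualifying.

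**What to change.** Reconcile Sections 7 and 9 with the objective in Section 3 by stating that:

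1. the interim decision is made separately in each condition;
2. a result in one condition does not close the others;
3. the dose comparison in a condition is stopped early only on the 10 mg versus 30 mg contrast;
4. a ketorolac-versus-saline result does not by itself end the dose comparison.

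The sponsor may consider closing only the saline arm in a condition where the saline contrast is met. That is one option and not a necessary part of the change.

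**Cost.** Points 1 to 4 are an amendment of wording and need no patients beyond those planned. There would be fewer early stops and more interim decisions to specify, each needing a stated test and boundary. If a saline arm is closed, randomisation and drug supply change for that condition, and later patients there have no concurrent saline comparison.
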